5. AMENDMENTS

Notable changes to the SAP that were completed prior to finalization are given below. Minor changes, clarifications and corrections are not listed.

Date	Section	Description of Change
------	---------	-----------------------

7. ATTACHMENTS AND APPENDICES

Appendix 1 Adverse Events of Special Interest – Abuse Liability

Withdrawal	Drug withdrawal convulsions
	Drug withdrawal headache
	Drug withdrawal maintenance therapy
	Drug withdrawal syndrome
	Drug withdrawal syndrome neonatal
	Drug rehabilitation
	Rebound effect
	Steroid withdrawal syndrome
	Withdrawal arrhythmia
	Withdrawal syndrome
Drug abuse and dependence	Dopamine dysregulation syndrome
	Drug abuse
	Drug abuser
	Drug dependence
	Drug dependence, antepartum
	Drug dependence, postpartum
	Intentional drug misuse
	Intentional overdose
	Maternal use of illicit drugs
	Neonatal complications of substance abuse
	Polysubstance dependence
	Substance abuse
	Substance abuser
	Accidental overdose
	Dependence
	Disturbance in social behaviour
	Drug administered at inappropriate site
	Drug detoxification
	Drug diversion
	Drug level above therapeutic
	Drug level increased
	Drug screen
	Drug screen positive
	Drug tolerance
	Drug tolerance decreased
	Drug tolerance increased
	Medication overuse headache
	Narcotic bowel syndrome
	Needle track marks
	Overdose
	Prescribed overdose
	Prescription form tampering
	Substance use
	Substance-induced mood disorder
Substance-induced psychotic disorder	
Toxicity to various agents	

Appendix 2 Ranges for Clinically Significant Changes and Other Defined Flagged Values in Vital Signs

The range of values that will be used to identify clinically significant changes in vital signs parameters (See Section 4.5.8.1) are presented in Table 7.

Table 7 Ranges for Clinically Significant Changes in Vital Signs

Vital Sign	Range
Sitting Systolic BP	Change: < -20, > 20
Sitting Diastolic BP	Change: < -10, > 10
Pulse Rate	Change: < -15, > 15
Weight	Percent Change: $\leq -7, \geq 7$

Defined flagged values that will be used to identify low or high vital signs parameters (See Section 4.5.8.1) are presented in Table 8.

Table 8 Other Defined Flagged Values for Vital Signs

Vital Sign	Flag
Sitting Systolic BP	< 90, > 140, > 160
Sitting Diastolic BP	< 50, > 90, > 100
Pulse Rate	< 60, > 100
Temperature	> 38.0, < 36.0
Respiratory Rate	< 12, > 20

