9.1.15.1.1 List of 'Triggering Adverse Events of Interest'

During the collection of AEs, if the patient reports an AE consistent with any of the following categories, then the Investigator or study coordinator is required to complete an additional Supplemental Adverse Event Form and a Site Classification Form (Investigator only) following further discussion of the event(s) with the patient or their caregiver. The categories are:

- Euphoria or inappropriate elation.
- Inappropriate laughter or exhilaration.
- Mood changes.
- Drunk, high or intoxicated.
- Hallucinations (visual or auditory), dissociations, disorientation, agitation.
- Disturbance in cognition, memory, or attention.
- Drug abuse.
- Drug withdrawal or drug withdrawal syndrome.

- Addiction.
- Overdose.
- Misuse of IMP.
- Thoughts of suicide, attempted suicide or suicide.

An AE that is consistent with the above categories will be known as a ‘triggering AE of interest’ for the purposes of this study.

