9.1.15.5 Adjudication Committee: Assessment of Abuse Potential of GWP42003-P

A formal Adjudication Committee will be appointed and assigned to this initiative to classify triggered cases. The Adjudication Committee will meet on a periodic basis to review and assess all of the information collected on triggered cases.

[figure not shown]
A detailed charter will be agreed, which will describe the roles, responsibilities and duties of the members of Adjudication Committee. The Committee will review all of the information collected in the process and in the assessment of the abuse potential of GWP42003-P, such as:

- All triggering AE information.
- Supplemental Adverse Event Form (if applicable).
- All triggering drug accountability discrepancies.
- Supplemental Drug Accountability Form (if applicable).
- Site Classification Form.
- Study Medication Use and Behavioral Survey.
- Additional information from site(s) as requested by the Committee.

The Adjudication Committee will assess all of the information. It will form a position on the classification of each event and will write a study-related report, detailing the conclusions and recommendations.

The overall process is summarized in [Figure 9-1](#).

Figure 9-1 Flow Diagram for Identifying and Evaluating Clinical Trial Adverse Event Data Through Systematic Categorization, Tabulation and Analysis which can Illuminate an Abuse Potential Signal (for Patients 12 Years of Age and Older)

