- Change in growth and development for patients less than 18 years of age by measurement of height, weight, insulin-like growth factor-1 (IGF-1) levels and Tanner Staging (for patients aged 10–17 [inclusive], or earlier if clinically indicated by onset of menarche or other signs of precocious puberty), relative to the pre-randomization baseline of the Core Study.
- Effects on menstruation cycles (in females).
- Drug abuse liability, as measured by AEs of abuse potential, drug accountability and Study Medication Use and Behavior Survey in patients aged 12 and older.

DS Patients Only:

- Percentage change in total convulsive seizure frequency, relative to the pre-randomization baseline of the Core Study.
- Percentage change in total non-convulsive seizure frequency, relative to the pre-randomization baseline of the Core Study.
- Number of patients considered treatment responders, defined as those with a $\geq 25\%$, $\geq 50\%$, $\geq 75\%$, or 100% reduction in convulsive seizures, relative to the pre-randomization baseline of the Core Study.
- Number of patients experiencing a $> 25\%$ worsening, $- 25$ to $+ 25\%$ no change, 25–50% improvement, 50–75% improvement or $> 75\%$ improvement in convulsive seizures, relative to the pre-randomization baseline of the Core Study.

LGS Patients Only:

- Percentage change in the number of drop seizures, relative to the pre-randomization baseline of the Core Study.
- Percentage change in the number of non-drop seizures, relative to the pre-randomization baseline of the Core Study.
- Number of patients considered treatment responders, defined as those with a $\geq 25\%$, $\geq 50\%$, $\geq 75\%$, or 100% reduction in drop seizures, relative to the pre-randomization baseline of the Core Study.
- Number of patients experiencing a $> 25\%$ worsening, $- 25$ to $+ 25\%$ no change, 25–50% improvement, 50–75% improvement or $> 75\%$ improvement in drop seizures, relative to the pre-randomization baseline of the Core Study.

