- Weeks 3 to 6 (Day 15 to 42).
- Weeks 7 to 10 (Day 43 to 70).
- Weeks 11 to 14 (Day 71 to 98).
- >14 weeks (> Day 98).

The time to first onset of AE will be calculated for TEAEs as:

$$\text{Start date of AE} - \text{Date of first dose of OLE IMP} + 1$$

If patients have multiple occurrences of an AE then the AE will be counted once for the first occurrence only. Percentages will be based on the number of patients in the safety analysis set who have a visit or follow-up call within each time period above.

For the summary of TEAEs by time to AE resolution, data will be summarized under the following categories:

- 1 week (≤ 7 days).
- 2 weeks (8 to 14 days).
- 3 weeks (15 to 21 days).
- 4 weeks (22 to 28 days).
- >4 weeks (>28 days).
- Ongoing (for AEs not resolved).

The time to AE resolution will be calculated for TEAEs as:

$$\text{Stop date of AE} - \text{Start date of AE} + 1$$

If patients have multiple occurrences of an AE then the AE will be counted once for the occurrence with the longest time to AE resolution. However, if any of the AEs are not resolved, then the AE will be counted once within the 'Ongoing' category.

For time of first onset of AE and time to AE resolution, partial or missing dates will be handled according to Section 4.1.2.2. If an AE has a partial start date and it is unclear from the partial date (or the stop date) whether the AE started prior to or post first dose of IMP then the start date will be imputed as the date of first dose of IMP in the OLE (Day 1). The start and stop day of the AE relative to the first dose of IMP (as recorded on the CRF) will be calculated as per Section 4.1.3. For partial dates, if it is clear from the partial date that

the start/stop day was prior to the first dose of IMP, then 'pre' will be listed, similarly if it is clear that the event was post the first dose of IMP then 'post' will be listed as the start/stop day as appropriate.

All AEs will be listed. Listings will include the start and stop day of the AE, a flag for treatment emergence, and limited demographic information about the patient (age, sex, race and weight at screening). A separate listing will be provided for pre-treatment AEs, serious AEs and events of special interest (see [Appendix 1](#)).

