Table 13.1.1	Summary of Laboratory Safety Parameters – Hematology	Safety Analysis Set
Table 13.1.2	Summary of Laboratory Safety Parameters – Biochemistry	Safety Analysis Set
Table 13.2.1	Shift Table for Hematology Laboratory Parameters – Based on Reference Ranges	Safety Analysis Set
Table 13.2.2	Shift Table for Biochemistry Laboratory Parameters – Based on Reference Ranges	Safety Analysis Set
Table 13.3.1	Shift Table for Hematology Laboratory Parameters – Based on Toxicity Limits	Safety Analysis Set
Table 13.3.2	Shift Table for Biochemistry Laboratory Parameters – Based on Toxicity Limits	Safety Analysis Set
Table 13.4	Incidence of Hy’s Law Cases	Safety Analysis Set
Table 14.1.1	Summary of Vital Signs	Safety Analysis Set
Table 14.1.2	Incidence of Clinically Significant Changes from Baseline for Vital Signs	Safety Analysis Set
Table 14.1.3	Incidence of Defined Flagged Vital Signs	Safety Analysis Set
Table 14.2.1	Summary of ECG Parameters	Safety Analysis Set
Table 14.2.2	Incidence of Defined Flagged ECG Parameter Values	Safety Analysis Set
Table 14.3	Summary of Patients with Inpatient Hospitalizations due to Epilepsy	Safety Analysis Set
Table 14.4.1	Summary of Children’s Columbia-Suicide Severity Rating Scale	Safety Analysis Set
Table 14.4.2	Summary of Children’s Columbia-Suicide Severity Rating Scale by Type	Safety Analysis Set
Table 14.5	Summary of Tanner Stages	Safety Analysis Set
Table 14.6	Summary of Menstruation Details	Safety Analysis Set
Table 14.7	Summary of Cannabis Withdrawal Scale (18 Years and Above)	Safety Analysis Set
Table 14.8	Summary of Pediatric Cannabinoid Withdrawal Scale (4–17 Years)	Safety Analysis Set
Table 14.9	Summary of Study Medication Use and Behavior Survey	Safety Analysis Set
Table 14.10.1	Summary of Supplemental Drug Accountability Form	Safety Analysis Set
Table 14.10.2	Summary of Supplemental Adverse Event Form	Safety Analysis Set
Table 14.10.3	Summary of Site Classification Form	Safety Analysis Set

Table 13 List of Listings

Listing Number	Title	Analysis Set
Listing 1.1.1	Patient Disposition – End of Treatment	Safety Analysis Set
Listing 1.1.2	Patient Disposition – End of Taper	Safety Analysis Set
Listing 1.2	Inclusion/Exclusion Criteria Not Met	Safety Analysis Set
Listing 1.3	Visit Dates	Safety Analysis Set
Listing 2.1.1	Important Protocol Deviations	All Randomized Patients
Listing 2.1.2	All Protocol Deviations	All Randomized Patients
Listing 2.2	Analysis Sets	All Randomized Patients

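### The SAP's abuse-liability term list has no direct term for 7 of the protocol's 12 triggering-AE categories, and no table gives abuse-potential AEs by category in patients aged 12 and older

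*SAP*

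**What the plan says.** SAP 3.3.2 keeps the endpoint in the protocol's terms: "Drug abuse liability, as measured by AEs of abuse potential, drug accountability and Study Medication Use and Behavior Survey in patients aged 12 and older". SAP 4.7, which names the protocol endpoints that are dropped, does not name this one. Protocol 13.6.3 includes it among the secondary endpoints to be summarized across time with descriptive methods.

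The two documents describe abuse-related AEs in two ways:

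- Protocol 9.1.15.1.1 gives 12 categories that oblige the site to complete a Supplemental Adverse Event Form. They include "Euphoria or inappropriate elation" and "Hallucinations (visual or auditory), dissociations, disorientation, agitation". SAP 4.6.5 repeats all 12.
- The SAP's "Appendix 1 Adverse Events of Special Interest", subtitled Abuse Liability, gives a list of terms under two headings, Withdrawal and Drug abuse and dependence.

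For the second set, SAP 4.5.2 says: "A separate listing will be provided for pre-treatment AEs, serious AEs and events of special interest". In Appendix 5 this becomes Listing 11.1.2, with no matching table. For the first set, SAP 4.6.5 summarizes the number of patients with a form (Table 14.10.2). SAP 4.6.6 summarizes the site's classification, relationship and certainty (Table 14.10.3, "Summary of Site Classification Form").

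**The concern.** A reader of the final report who looks for abuse-liability AEs will go first to the output that carries that label. As the SAP stands, that output is a listing built from withdrawal, abuse and dependence terms. The psychoactive effects that the protocol itself treats as signals of abuse potential have no direct terms in it. The labelled output could therefore be nearly empty while euphoria, intoxication or hallucination events were reported under other titles.

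The endpoint also lacks a basic number: how many patients aged 12 and older had at least one AE of abuse potential, by kind of event. What is at stake is whether a retained secondary endpoint gets the summary that the protocol promises, under a definition consistent with the protocol.

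**Working it through.** The study is descriptive and the plan states no figure for this point, so the check is a count followed by a search for other outputs.

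**Step 1. Size of the list.** Appendix 1 has 10 terms under Withdrawal and 36 under Drug abuse and dependence: 10 + 36 = 46.

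**Step 2. Match each category to the 46 terms, by keyword and meaning.**

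| Triggering category (short form) | Direct term in Appendix 1 | Adjacent term |
|---|---|---|
| Euphoria, elation | none | none |
| Laughter, exhilaration | none | none |
| Mood changes | none | Substance-induced mood disorder |
| Drunk, high, intoxicated | none | Toxicity to various agents |
| Hallucination, dissociation, disorientation, agitation | none | Substance-induced psychotic disorder |
| Cognition, memory, attention | none | none |
| Drug abuse | yes | |
| Withdrawal | yes | |
| Addiction | yes (dependence terms) | |
| Overdose | yes | |
| Misuse | yes | |
| Suicidality | none | none |

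**Step 3. Count.** Direct match: 5 of 12. No direct match: 12 − 5 = 7. If the three adjacent terms are accepted as matches, 7 − 3 = 4 categories remain with nothing. If suicidality is instead left to the C-SSRS, the strict count is 7 − 1 = 6. The adjacent terms are weak substitutes. Two presuppose a substance-induced diagnosis and the third is a toxicity term, so an AE coded simply as euphoria or hallucination would not be retrieved.

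**Step 4. Look for the seven categories elsewhere in the SAP.**

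- Table 14.10.2 and Listing 14.12.2: all 12 categories trigger a form. SAP 4.6.5 specifies only the number of patients with a form, with no split by category.
- Table 14.10.3 and Listing 14.12.3: these show the classification assigned by the site, and pool forms triggered by AEs with forms triggered by drug accountability. Neither document says that these classifications are the 12 trigger categories.
- Table 11.2: all TEAEs by system organ class and preferred term, at all ages. A patient with two terms from one category appears under both, so patients per category cannot be recovered, nor can the group aged 12 and older be separated.
- Tables 14.4.1 and 14.4.2: suicidality from the C-SSRS.

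So none of the 12 categories is wholly absent from the outputs, and none of the planned tables gives incidence by triggering category.

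**Step 5. Denominator.** Protocol 9.1.15 confines this monitoring to patients aged 12 and older. Appendix 5 assigns Tables 14.10.1 to 14.10.3 to the Safety Analysis Set, which includes the 2–5 and 6–11 age groups of SAP 4.4.4. SAP 4.6.1 states a denominator for the survey, but SAP 4.6.4 to 4.6.6 state none for these three forms. Whether percentages will appear, and on what base, is left open.

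**The case against.** The best defence is that Appendix 1 was never meant to define the endpoint. SAP 3.3.2 does not refer to it, and the only text that does is the sentence in SAP 4.5.2 on a separate listing. The protocol's actual instrument is the sequence of trigger, interview, site classification and adjudication, and the SAP carries the first three steps with all 12 categories intact. A preferred-term table could also mislead: protocol 3.1 describes attention, mood and behavioral disorders as common in these syndromes, and a single-group study cannot separate them from a drug effect. Terms such as "Drug level above therapeutic" may over-include, but over-inclusion in a listing hides nothing.

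Much of this stands. It rules out three stronger conclusions that a reader might draw:

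- *That the endpoint would miss euphoria, intoxication, hallucination or cognition events.* It would not. They trigger forms that are counted and site-classified, and they appear in the general TEAE tables.
- *That rates are diluted by a known factor because unmonitored children are in the denominator.* The documents give neither the age split nor the denominator, and SAP 4.6.4 and 4.6.5 promise counts of patients, which are not diluted.
- *That adjudication goes unreported.* The SAP plans no output for it, but protocol 9.1.15.5 says of the committee: "It will form a position on the classification of each event and will write a study-related report". The protocol also does not say that its classifications are entered in the CRF, so they may not be in the analysis database.

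The defence does not remove the mismatch. The SAP labels a list Abuse Liability that disagrees with its own section 4.6.5, and the form counts do not supply the missing summary by category. Form completion also depends on the site recognizing a trigger. A preferred-term search would be an independent check on that, and for seven categories Appendix 1 cannot provide one.

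**Conclusion.** The point holds as a moderate reporting and alignment defect. Seven of 12 protocol categories have no direct term in the SAP's abuse-liability list (four if adjacent terms are accepted). The listed events get no table. No planned output gives patients aged 12 and older with AEs of abuse potential by category, despite protocol 13.6.3. No data are lost, the primary safety summaries are unchanged, and the endpoint is descriptive.

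The conclusion rests on matching terms by their plain meaning, and on the Site Classification Form's categories not being the 12 triggers, which the documents leave unstated. If they are the same, Table 14.10.3 would give part of the missing summary, still pooled with accountability cases. No size can be put on the denominator question from the documents.

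**What to change.** 1. Extend Appendix 1 with preferred terms mapped to the 12 categories, keeping the present terms as the withdrawal and abuse/dependence groups. Suicidality may be cross-referenced to the C-SSRS tables. In that case, confirm that they cover adults, since the titles of Tables 14.4.1 and 14.4.2 name only the children's version.
2. Beside Listing 11.1.2, add one table of patients aged 12 and older with at least one such TEAE, by category, preferred term and indication. State whether age is taken at Visit 1, as SAP 4.4.4 computes it, or at onset of the event.
3. State that any percentages in Tables 14.10.1 to 14.10.3 are based on patients aged 12 and older.

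The cost is SAP wording, a longer term list, one table and a denominator statement, all from AE data already collected. The drawback is that more events, some of them due to the disease, will appear under abuse liability. The new table should therefore be read beside the site classifications in Table 14.10.3.

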Appendix 3 Defined Flagged Values in ECG Parameters

Defined flagged values that will be used to identify low or high ECG parameters (See Section 4.5.8.2) are presented in Table 9.

Table 9 Defined Flagged Values for ECG Parameters

ECG Parameter	Flag
QTc	> 450, > 480, > 500

Appendix 4 Toxicity Criteria for Laboratory Parameters

The toxicity criteria that will be used to identify abnormal laboratory parameters are presented in [Table 10](#) and [Table 11](#).

Table 10 Toxicity Criteria for Biochemistry Parameters

Parameter	Toxicity Decrease	Toxicity Increase
Chloride	≤0.96xLL	≥1.04xUL
Calcium	≤0.89xLL	≥1.16xUL
Sodium	≤0.96xLL	≥1.04xUL
Potassium	≤0.90xLL	≥1.10xUL
Glucose (mmol/L)	≤3.2	≥16
Phosphate	≤0.79xLL	
Cholesterol	≤0.85xLL	≥1.6xUL
ASAT (SGOT)		≥2.6xUL
ALAT (SGPT)		≥2.6xUL
Lactate Dehydrogenase (LDH)		≥2.6xUL
Alkaline phosphatase		≥2.6xUL
Gamma GT		≥2.6xUL
Bilirubin		≥1.26xUL
Albumin	≤0.84xLL	
Total protein	≤0.84xLL	≥1.16xUL
Urea		≥2.6xUL
Blood urea nitrogen (BUN)		≥2.6xUL
Creatinine		≥2.6xUL
Uric acid		≥1.16xUL

UL = upper limit of reference range

LL = lower limit of reference range

Table 11 Toxicity Criteria for Hematology Parameters

Parameter	Toxicity Decrease	Toxicity Increase
Hemoglobin (g/dL)	≤9.4	
Hematocrit (%)	≤28	
Red cell count	≤0.84xLL	
Mean corpuscular volume	≤0.84xLL	≥1.11xUL
Mean corpuscular hemoglobin	≤0.84xLL	
Mean corpuscular hemoglobin concentration	≤0.84xLL	
Platelets (x10 ⁹ /L)	≤74	
Prothrombin time		>1.5xUL
Prothrombin ratio		>1.5xUL
Total white blood cell count (x10 ⁹ /L)	≤2.9	≥21
Total neutrophil count (x10 ⁹ /L)	≤1.36	≥14.7
Segmented neutrophil count (x10 ⁹ /L)	≤0.75	≥12.3
Eosinophils (x10 ⁹ /L)		≥1.5
Basophils (x10 ⁹ /L)		≥0.31
Monocytes (x10 ⁹ /L)		≥2.1
Lymphocytes (x10 ⁹ /L) for patients <18 years (auto hematology)	≤1.0	
Lymphocytes (x10 ⁹ /L) for patients <18 years (manual hematology)	≤0.2	
Lymphocytes (x10 ⁹ /L) for patients ≥18 years	≤0.2	

Parameter	Toxicity Decrease	Toxicity Increase
Promyelocytes		≥1.1
Metamyelocytes (x10 ⁹ /L)		≥1.1
Mycloocytes (x10 ⁹ /L)		≥1.1

UL = upper limit of reference range LL = lower limit of reference range

Appendix 5 List of Tables, Listings and Figures

Lists of the tables, listings and figures to be provided are given below in [Table 12](#), [Table 13](#) respectively

Table 12 List of Tables

Table Number	Title	Analysis Set
Table 1.1	Summary of Patient Disposition – Numbers of Patients Enrolled, Withdrawn or Completed by Site	All Enrolled Patients
Table 1.2	Summary of Patient Disposition – Primary Reason for Withdrawals	All Enrolled Patients
Table 1.3	Summary of Withdrawals by Core Study and Visit	Safety Analysis Set
Table 2.1	Summary of Important Protocol Deviations	All Enrolled Patients
Table 2.2	Summary of Analysis Sets	All Enrolled Patients
Table 3.1	Summary of Demographic Data	Safety Analysis Set
Table 3.2	Summary of Baseline Characteristics	Safety Analysis Set
Table 5.1	Summary of Previous Significant Non-Epilepsy Medical or Surgical History Now Resolved	Safety Analysis Set
Table 5.2	Summary of Significant Non-Epilepsy Medical or Surgical History – Current Conditions	Safety Analysis Set
Table 6.1	Summary of Concomitant Antiepileptic Therapies	Safety Analysis Set
Table 6.2	Summary of Concomitant Antiepileptic Medications	Safety Analysis Set
Table 6.3	Summary of Concomitant Rescue Medications	Safety Analysis Set
Table 6.4	Summary of Other Concomitant Medications	Safety Analysis Set
Table 9.1.1.1	Summary of Total Seizure Frequency	Safety Analysis Set
Table 9.1.1.2	Summary of Total Seizure Frequency (LOCF)	Safety Analysis Set
Table 9.1.2.1	Summary of Drop Seizure Frequency	Safety Analysis Set
Table 9.1.2.2	Summary of Drop Seizure Frequency (LOCF)	Safety Analysis Set
Table 9.1.3.1	Summary of Convulsive Seizure Frequency	Safety Analysis Set
Table 9.1.3.2	Summary of Convulsive Seizure Frequency (LOCF)	Safety Analysis Set
Table 9.2	Summary of Patients with Status Epilepticus	Safety Analysis Set
Table 9.3.1	Summary of the Subject/Caregiver Global Impression of Change	Safety Analysis Set
Table 9.3.2	Summary of Subject/Caregiver Global Impression of Change in Seizure Duration	Safety Analysis Set
Table 9.4.1.1	Summary of Total Seizure Frequency - Patients Taking Clobazam	Safety Analysis Set
Table 9.4.1.2	Summary of Total Seizure Frequency - Patients Not Taking Clobazam	Safety Analysis Set
Table 9.4.2.1	Summary of Drop Seizure Frequency - Patients Taking Clobazam	Safety Analysis Set
Table 9.4.2.2	Summary of Drop Seizure Frequency - Patients Not Taking Clobazam	Safety Analysis Set
Table 9.4.3.1	Summary of Convulsive Seizure Frequency - Patients Taking Clobazam	Safety Analysis Set

Table Number	Title	Analysis Set
Table 9.4.3.2	Summary of Convulsive Seizure Frequency - Patients Not Taking Clobazam	Safety Analysis Set
Table 9.5.1.1	Summary of Total Seizure Frequency - Core Study Actual Treatment of Placebo	Safety Analysis Set
Table 9.5.1.2	Summary of Total Seizure Frequency - Core Study Actual Treatment of Active	Safety Analysis Set
Table 9.5.2.1	Summary of Drop Seizure Frequency - Core Study Actual Treatment of Placebo	Safety Analysis Set
Table 9.5.2.2	Summary of Drop Seizure Frequency - Core Study Actual Treatment of Active	Safety Analysis Set
Table 9.5.3.1	Summary of Convulsive Seizure Frequency - Core Study Actual Treatment of Placebo	Safety Analysis Set
Table 9.5.3.2	Summary of Convulsive Seizure Frequency - Core Study Actual Treatment of Active	Safety Analysis Set
Table 9.5.4.1	Summary of Total Seizure Frequency - Core Study Actual Treatment of Placebo and Taking Clobazam	Safety Analysis Set
Table 9.5.4.2	Summary of Total Seizure Frequency - Core Study Actual Treatment of Placebo and Not Taking Clobazam	Safety Analysis Set
Table 9.5.4.3	Summary of Total Seizure Frequency - Core Study Actual Treatment of Active and Taking Clobazam	Safety Analysis Set
Table 9.5.4.4	Summary of Total Seizure Frequency - Core Study Actual Treatment of Active and Not Taking Clobazam	Safety Analysis Set
Table 9.5.5.1	Summary of Drop Seizure Frequency - Core Study Actual Treatment of Placebo and Taking Clobazam	Safety Analysis Set
Table 9.5.5.2	Summary of Drop Seizure Frequency - Core Study Actual Treatment of Placebo and Not Taking Clobazam	Safety Analysis Set
Table 9.5.5.3	Summary of Drop Seizure Frequency - Core Study Actual Treatment of Active and Taking Clobazam	Safety Analysis Set
Table 9.5.5.4	Summary of Drop Seizure Frequency - Core Study Actual Treatment of Active and Not Taking Clobazam	Safety Analysis Set
Table 9.5.6.1	Summary of Convulsive Seizure Frequency - Core Study Actual Treatment of Placebo and Taking Clobazam	Safety Analysis Set
Table 9.5.6.2	Summary of Convulsive Seizure Frequency - Core Study Actual Treatment of Placebo and Not Taking Clobazam	Safety Analysis Set
Table 9.5.6.3	Summary of Convulsive Seizure Frequency - Core Study Actual Treatment of Active and Taking Clobazam	Safety Analysis Set
Table 9.5.6.4	Summary of Convulsive Seizure Frequency - Core Study Actual Treatment of Active and Not Taking Clobazam	Safety Analysis Set

Table Number	Title	Analysis Set
Table 9.5.7.1	Summary of Drop Seizure Frequency - Patients with Week 37 to 48 Data	Safety Analysis Set
Table 9.5.7.2	Summary of Convulsive Seizure Frequency - Patients with Week 37 to 48 Data	Safety Analysis Set
Table 9.5.7.3	Summary of Drop Seizure Frequency - Patients Taking Clobazam - Patients with Week 37 to 48 Data	Safety Analysis Set
Table 9.5.7.4	Summary of Drop Seizure Frequency - Patients Not Taking Clobazam - Patients with Week 37 to 48 Data	Safety Analysis Set
Table 9.5.7.5	Summary of Convulsive Seizure Frequency - Patients Taking Clobazam - Patients with Week 37 to 48 Data	Safety Analysis Set
Table 9.5.7.6	Summary of Convulsive Seizure Frequency - Patients Not Taking Clobazam - Patients with Week 37 to 48 Data	Safety Analysis Set
Table 9.7.1	Summary of Responder Rates for Total Seizure Frequency	Safety Analysis Set
Table 9.7.2	Summary of Responder Rates for Total Seizure Frequency (LOCF)	Safety Analysis Set
Table 9.7.3	Summary of Responder Rates for Drop Seizure Frequency	Safety Analysis Set
Table 9.7.4	Summary of Responder Rates for Drop Seizure Frequency (LOCF)	Safety Analysis Set
Table 9.7.5	Summary of Responder Rates for Convulsive Seizure Frequency	Safety Analysis Set
Table 9.7.6	Summary of Responder Rates for Convulsive Seizure Frequency (LOCF)	Safety Analysis Set
Table 9.15.1.1	Summary of Quality of Life in Childhood Epilepsy Scores (2-18 Years)	Safety Analysis Set
Table 9.15.2	Summary of Quality of Life in Epilepsy Scores (19 Years and Above)	Safety Analysis Set
Table 9.16.1.1	Summary of the Vineland-II Adaptive Behavior Subdomain, Domain and Composite Scores	Safety Analysis Set
Table 9.16.1.2	Summary of the Vineland-II Adaptive Behavior Subdomain, Domain and Composite Adaptive Levels	Safety Analysis Set
Table 9.16.2.1	Summary of the Vineland-II Maladaptive Behavior Subdomain and Index Scores	Safety Analysis Set
Table 9.16.2.2	Summary of the Vineland-II Maladaptive Behavior Subdomain and Index Adaptive Levels	Safety Analysis Set
Table 9.17.1	Summary of Cognitive Assessment Battery Patient Measures	Safety Analysis Set
Table 9.17.2.1	Summary of Cognitive Assessment Battery Parent Measures - Executive (Behavior Rating Inventory of Executive Function)	Safety Analysis Set
Table 9.17.2.2	Summary of Cognitive Assessment Battery Parent Measures - Attention (ADHD Checklist)	Safety Analysis Set
Table 9.17.2.3	Summary of Cognitive Assessment Battery Parent Measures - Mood/Anxiety (BASC-2)	Safety Analysis Set

Table Number	Title	Analysis Set
Table 9.17.2.4	Summary of Cognitive Assessment Battery Parent Measures - Behavior Report Form	Safety Analysis Set
Table 10.1	Summary of Exposure	Safety Analysis Set
Table 10.2	Summary of Exposure - Excluding Study GWEP1332 Part A	Safety Analysis Set
Table 10.3.1	Summary of Exposure - Patients Taking Clobazam	Safety Analysis Set
Table 10.3.2	Summary of Exposure - Patients Not Taking Clobazam	Safety Analysis Set
Table 10.4.1	Summary of Exposure - Core Study Actual Treatment of Placebo	Safety Analysis Set
Table 10.4.2	Summary of Exposure - Core Study Actual Treatment of Active	Safety Analysis Set
Table 10.5.1	Summary of Exposure - Core Study Actual Treatment of Placebo and Taking Clobazam	Safety Analysis Set
Table 10.5.2	Summary of Exposure - Core Study Actual Treatment of Placebo and Not Taking Clobazam	Safety Analysis Set
Table 10.5.3	Summary of Exposure - Core Study Actual Treatment of Active and Taking Clobazam	Safety Analysis Set
Table 10.5.4	Summary of Exposure - Core Study Actual Treatment of Active and Not Taking Clobazam	Safety Analysis Set
Table 10.6	Summary of Patient-years (On Treatment) by Modal Dose Group	Safety Analysis Set
Table 11.1	Overall Summary of Treatment Emergent Adverse Events	Safety Analysis Set
Table 11.2	Summary of Treatment Emergent Adverse Events	Safety Analysis Set
Table 11.3	Summary of Treatment-Related Treatment Emergent Adverse Events	Safety Analysis Set
Table 11.4	Summary of Treatment Emergent Adverse Events by Maximal Severity	Safety Analysis Set
Table 11.5	Summary of Treatment Emergent Adverse Events by Sex	Safety Analysis Set
Table 11.6	Summary of TEAEs by Time of First Onset of AE	Safety Analysis Set
Table 11.7	Summary of TEAEs by Time to AE Resolution	Safety Analysis Set
Table 11.8	List of Patients Experiencing Treatment Emergent Adverse Events by System Organ Class and Preferred term	Safety Analysis Set
Table 12.1	Summary of Serious Treatment Emergent Adverse Events	Safety Analysis Set
Table 12.2	Summary of Treatment-Related Serious Treatment Emergent Adverse Events	Safety Analysis Set
Table 12.3	Summary of Treatment Emergent Adverse Events Leading to Permanent Discontinuation of Study Medication	Safety Analysis Set
Table 12.4	Summary of Treatment-Related Treatment Emergent Adverse Events Leading to Permanent Discontinuation of Study Medication	Safety Analysis Set

Table Number	Title	Analysis Set
Table 12.5	Summary of Fatal Treatment Emergent Adverse Events	Safety Analysis Set
Table 13.1.1	Summary of Laboratory Safety Parameters – Hematology	Safety Analysis Set
Table 13.1.2	Summary of Laboratory Safety Parameters – Biochemistry	Safety Analysis Set
Table 13.2.1	Shift Table for Hematology Laboratory Parameters – Based on Reference Ranges	Safety Analysis Set
Table 13.2.2	Shift Table for Biochemistry Laboratory Parameters – Based on Reference Ranges	Safety Analysis Set
Table 13.3.1	Shift Table for Hematology Laboratory Parameters – Based on Toxicity Limits	Safety Analysis Set
Table 13.3.2	Shift Table for Biochemistry Laboratory Parameters – Based on Toxicity Limits	Safety Analysis Set
Table 13.4	Incidence of Hy’s Law Cases	Safety Analysis Set
Table 14.1.1	Summary of Vital Signs	Safety Analysis Set
Table 14.1.2	Incidence of Clinically Significant Changes from Baseline for Vital Signs	Safety Analysis Set
Table 14.1.3	Incidence of Defined Flagged Vital Signs	Safety Analysis Set
Table 14.2.1	Summary of ECG Parameters	Safety Analysis Set
Table 14.2.2	Incidence of Defined Flagged ECG Parameter Values	Safety Analysis Set
Table 14.3	Summary of Patients with Inpatient Hospitalizations due to Epilepsy	Safety Analysis Set
Table 14.4.1	Summary of Children’s Columbia-Suicide Severity Rating Scale	Safety Analysis Set
Table 14.4.2	Summary of Children’s Columbia-Suicide Severity Rating Scale by Type	Safety Analysis Set
Table 14.5	Summary of Tanner Stages	Safety Analysis Set
Table 14.6	Summary of Menstruation Details	Safety Analysis Set
Table 14.7	Summary of Cannabis Withdrawal Scale (18 Years and Above)	Safety Analysis Set
Table 14.8	Summary of Pediatric Cannabinoid Withdrawal Scale (4–17 Years)	Safety Analysis Set
Table 14.9	Summary of Study Medication Use and Behavior Survey	Safety Analysis Set
Table 14.10.1	Summary of Supplemental Drug Accountability Form	Safety Analysis Set
Table 14.10.2	Summary of Supplemental Adverse Event Form	Safety Analysis Set
Table 14.10.3	Summary of Site Classification Form	Safety Analysis Set

Table 13 List of Listings

Listing Number	Title	Analysis Set
Listing 1.1.1	Patient Disposition – End of Treatment	Safety Analysis Set
Listing 1.1.2	Patient Disposition – End of Taper	Safety Analysis Set
Listing 1.2	Inclusion/Exclusion Criteria Not Met	Safety Analysis Set
Listing 1.3	Visit Dates	Safety Analysis Set
Listing 2.1.1	Important Protocol Deviations	All Randomized Patients
Listing 2.1.2	All Protocol Deviations	All Randomized Patients
Listing 2.2	Analysis Sets	All Randomized Patients
Listing 3.1	Demography	Safety Analysis Set
Listing 3.2	Baseline Characteristics	Safety Analysis Set
Listing 5	Significant Non-Epilepsy Medical or Surgical History	Safety Analysis Set
Listing 6.1	History of Antiepileptic Medications	Safety Analysis Set
Listing 6.2	Prior and Concomitant Antiepileptic Therapies	Safety Analysis Set
Listing 6.3	Prior and Concomitant Antiepileptic Medications	Safety Analysis Set
Listing 6.4	Prior and Concomitant Rescue Medications	Safety Analysis Set
Listing 6.5	Other Prior and Concomitant Medications	Safety Analysis Set
Listing 9.1.1	IVRS Diary Data – Part 1	Safety Analysis Set
Listing 9.1.2	IVRS Diary Data – Part 2	Safety Analysis Set
Listing 9.2	Derived Drop, Convulsive and Total Seizure Data	Safety Analysis Set
Listing 9.3	Derived Status Epilepticus Data	Safety Analysis Set
Listing 9.4	Subject/Caregiver Global Impression of Change in Seizure Duration	Safety Analysis Set
Listing 9.5	Inpatient Hospitalizations due to Epilepsy	Safety Analysis Set
Listing 9.6	Subject/Caregiver Global Impression of Change	Safety Analysis Set
Listing 9.7.1	Quality of Life in Childhood Epilepsy (2-18 Years) - Derived Scores	Safety Analysis Set
Listing 9.7.2	Quality of Life in Epilepsy (19 Years and Above) - Derived Scores	Safety Analysis Set
Listing 9.8.1	Vineland-II Adaptive Behavior - Derived Data	Safety Analysis Set
Listing 9.8.2	Vineland-II Maladaptive Behavior - Derived Data	Safety Analysis Set
Listing 9.9.1.1	Cognitive Assessment Battery Patient Measures - Intelligence	Safety Analysis Set
Listing 9.9.1.2	Cognitive Assessment Battery Patient Measures - Attention/Executive	Safety Analysis Set
Listing 9.9.1.3	Cognitive Assessment Battery Patient Measures - Language, Visual-Spatial and Fine Motor Speed	Safety Analysis Set
Listing 9.9.2.1	Cognitive Assessment Battery Parent Measures - Executive (Behavior Rating Inventory of Executive Function)	Safety Analysis Set

Listing Number	Title	Analysis Set
Listing 9.9.2.2.1	Cognitive Assessment Battery Parent Measures - Attention (ADHD Checklist) - Part 1	Safety Analysis Set
Listing 9.9.2.2.2	Cognitive Assessment Battery Parent Measures - Attention (ADHD Checklist) - Part 2	Safety Analysis Set
Listing 9.9.2.3	Cognitive Assessment Battery Parent Measures - Mood/Anxiety (BASC-2)	Safety Analysis Set
Listing 9.9.2.4	Cognitive Assessment Battery Parent Measures - Behavior Report Form	Safety Analysis Set
Listing 10.1	Exposure	Safety Analysis Set
Listing 10.2	Exposure by Time	Safety Analysis Set
